4 STUDY DESIGN

4.1 Study Overview

This is a single center, prospective cohort study. Enrollment of approximately 98 patients is planned, 49 receiving whole blood and 49 receiving component therapy. This is an observational study planned during initiation of a change in practice at our institution initially allowing up to 4 units of whole blood transfusion for adult male trauma patients. If initial patients receiving whole blood show no evidence of hemolysis and thrombocytopenia compared to patients receiving component therapy, up to 6 units of whole blood transfusion will be allowed (see below, and section 5.2, Safety Evaluations). Patients in the whole blood, or index, group are adult male trauma patients presenting in hemorrhagic shock (systolic blood pressure < 100) requiring massive transfusion activation who receive whole blood for resuscitation. Two control groups will be utilized. The prospective control group consists of adult male patients who present during times when whole blood is not available, as well as adult female patients, presenting in hemorrhagic shock (systolic blood pressure <100) requiring massive transfusion activation. Additionally, a second control group consisting of historical

PI: [name]

controls receiving component therapy will be analyzed (see Section 6, Patient Selection, for details of index and control groups).

All patients will have, in addition to standard labs, additional labs drawn for thromboelastography, platelet function determination, and coagulation factor levels (see Section 9.1.6, Other Clinical Procedures, for details of specific lab tests and timing).

Patients who meet all inclusion criteria and none of the exclusion criteria will be enrolled into the study.

Total duration of patient participation will be approximately 1 year (365 days), or the duration of the hospital stay, whichever is shorter. This includes up to 5 days of laboratory testing during initial resuscitation and subsequent admission, and up to one year of follow up via chart review if the patient remains in the hospital. Total duration of the study including recruitment and follow up is expected to be 2 years.

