5.2 Safety Evaluations

- Hemolysis will be measured by haptoglobin, bilirubin, lactate dehydrogenase, and direct antiglobulin tests on ICU day 1. Clinical surveillance for evidence of hemolysis will also be ongoing. The Blood and Blood Derivatives committee will review data for the first 10 patients to receive whole blood for evidence of hemolysis and thrombocytopenia. If the risks of these conditions are judged by the Committee to be equivalent to risks seen following treatment with similar amounts of component therapy, the Committee will allow an increase from up to 4 units to up to 5 units of whole blood to be transfused. After 10 patients have received whole blood under this protocol, the Committee will again evaluate for hemolysis and thrombocytopenia and increase to a maximum of 6 units of whole blood if risks are found to be equivalent to component therapy.
- Alternatively, should the safety of up to 4 units of whole blood be published before 10 patients have received whole blood, the Committee will allow an increase to a maximum of 5 units of whole blood. The Committee will assess the first 10 patients to receive whole blood under this protocol and if the risks of hemolysis and thrombocytopenia are judged by the Committee to be equivalent to risks seen following treatment with similar amounts of component therapy, the Committee will allow up to 6 units of whole blood to be transfused.
- The Blood and Blood Derivatives Committee at UCLA, also known as the Transfusion Committee, is composed of Transfusion Medicine faculty members. The Committee performs routine monthly monitoring of all transfusion-related safety

PI: [name]

data, including evidence of hemolysis and other transfusion reactions. In addition, the Committee has agreed to perform a separate evaluation of the cohort of patients receiving whole blood and compare this to equivalent patients receiving component therapy (as defined in the inclusion and exclusion criteria for the study), for the purposes of evaluating the safety of whole blood. [name], who are co-investigators in this study, are members of the Blood and Blood Derivatives Committee but will be recused from safety analysis related to this study to prevent conflict of interest. No other member of the Committee has a relationship to the study.

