- The incidence of adverse events will be evaluated including: death, clinical coagulopathy, hemolysis, infection, venous thromboembolism, cerebrovascular accident, acute coronary syndrome, transfusion-related lung injury, transfusion-associated cardiac overload.
- The occurrence of any whole blood transfusion given to patients other than adult male trauma patients will also be recorded
- In addition to ongoing monitoring and final analysis, an interim safety analysis when approximately 50% of patients have been enrolled will determine if there is a difference in adverse events as defined above between groups.
- The interim analysis will be performed by the independent medical monitor. The independent medical monitor, [name], is an emergency medicine physician with extensive experience in clinical investigation and has no relation to the study other than to monitor safety. The independent medical monitor has the authority to stop the study if safety concerns arise, including but not limited to evidence for the pre-specified stopping criteria (see Section 12.5, Stopping Criteria). [name] is also independent of the Blood and Blood Derivatives Committee.

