15.4 Analysis of Secondary Endpoints

Continuous variables and categorical variables will be analyzed as described above (section 15.3). Mixed effects linear regression models will be used to evaluate coagulopathy over time and to adjust for confounding variables.

To analyze coagulopathy over time we will use a mixed effects linear regression model. A mixed effects linear regression model will also be used to adjust for confounding variables such as sex, age, comorbidities, severity of injury, and physiologic parameters of shock including pH and temperature, and use of a rapid transfuser (which more effectively warms blood).

Quarterly safety monitoring will compare categorical variables including mortality and development of complications (duration of need for renal replacement therapy,

PI: [name]

mechanical ventilation, ICU admission, and hospital stay; clinical coagulopathy, infection, venous thromboembolism, cerebrovascular accident, acute coronary syndrome, transfusion-related lung injury, transfusion-associated cardiac overload; transfusion reactions including clinical transfusion reactions and rates of hemolysis as measured by haptoglobin, bilirubin, lactate dehydrogenase, and direct antiglobulin). Categorical variables will be compared using the chi-squared test.

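### Section 5.2's publication route to 5 units does not make a review of the whole blood patients already treated a condition of the increase

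*Protocol*

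**What the plan says.** Section 5.2 of the protocol sets the rules for raising the cap. Its first bullet gives the main route: "The Blood and Blood Derivatives committee will review data for the first 10 patients to receive whole blood for evidence of hemolysis and thrombocytopenia". Where the Committee judges those risks equivalent to the risks with comparable amounts of component therapy, the cap goes from 4 to 5 units. A further evaluation, once 10 patients have received whole blood, governs the rise to 6.

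The second bullet gives the alternative: "should the safety of up to 4 units of whole blood be published before 10 patients have received whole blood, the Committee will allow" a maximum of 5 units. In this bullet the assessment of the first 10 patients appears only as the condition for 6 units.

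Section 4.1 summarizes the rise above 4 units in terms of the study's own patients: "If initial patients receiving whole blood show no evidence of hemolysis and thrombocytopenia compared to patients receiving component therapy", up to 6 units will be permitted. It does not mention publication, but it refers the reader to section 5.2.

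Several other safety checks run alongside:

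- Section 5.2: the Committee's monthly monitoring of transfusion safety "data, including evidence of hemolysis and other transfusion reactions".
- Section 5.2: a commitment without stated timing, in that "the Committee has agreed to perform a separate evaluation of the cohort of patients receiving whole blood".
- Section 15.4: quarterly comparisons that include "rates of hemolysis as measured by haptoglobin, bilirubin, lactate dehydrogenase, and direct antiglobulin".
- Section 10.1 and Appendix I: platelet counts at least daily, and hemolysis labs on ICU day 1.
- Sections 11.1 and 14: adverse event review, with abnormal laboratory findings counted as adverse events.
- Section 12.5: a pause, and possibly a stop, after any hemolytic transfusion reaction to whole blood.
- Section 5.2: "The independent medical monitor has the authority to stop the study if safety concerns arise".

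**The concern.** The same one-unit step has two different conditions. On one route the Committee must look at its own patients and reach a comparative judgement. On the other, an outside publication is enough. Up to 9 patients may by then have had whole blood at this center, with hemolysis labs and platelet counts on file, and the rule does not ask anyone to consult those results before the cap rises.

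At stake is a modest safety point. If the early patients showed falling platelets, or laboratory hemolysis without the clinical syndrome that section 12.5 requires, the written condition for 5 units would still be met. The primary analysis and its error rate are not affected.

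**Working it through.** The plan states no figure to reproduce on this point. The check is a comparison of the two routes, with arithmetic to size the gap.

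**1. The routes side by side (section 5.2)**

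| | Main route | Publication route |
|---|---|---|
| Trigger for 4 to 5 units | 10 whole blood patients treated | Safety of up to 4 units published before the 10th |
| Own patients whose review is a condition | 10 | 0 |
| Judgement required | Equivalent to component therapy | None stated |
| 10-patient assessment before 6 units | Yes | Yes |

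**2. Is any other check a condition of the step?** The monthly monitoring, cohort evaluation, quarterly comparison, daily platelet counts, adverse event review, section 12.5 rule and medical monitor's authority were each read for a link to the cap. They cover hemolysis and, through platelet counts and adverse event review, low platelets. None is written as a condition of the publication-route rise.

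**3. Size of the step.** One unit, about 250 mL (section 8.3.1), and only if needed (section 8.4.1).

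**4. How long the branch stays open.** Inputs: 49 whole blood patients (section 4.1), and "Total duration of the study including recruitment and follow up is expected to be 2 years". Assumption: even accrual over 18 to 24 months, the shorter figure leaving room for follow-up.

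- Accrual: 49/24 = 2.04 per month; 49/18 = 2.72 per month.
- Time to the 10th whole blood patient: 10/2.04 = 4.9 months; 10/2.72 = 3.7 months.
- Patients treated by a first quarterly comparison at month 3: 3 × 2.04 = 6.1; 3 × 2.72 = 8.2.
- Patients not yet covered by a monthly check: from 0 just after a check to 2.0–2.7 just before the next, so on average 2.04/2 = 1.0 to 2.72/2 = 1.4.

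The branch is therefore open for roughly the first 4 to 5 months. During that time the routine monitoring would already have covered most treated patients.

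**5. What a review of few patients could show (illustration with assumed event rates).** With no events in n patients, the one-sided 95% upper bound on the risk is 1 − 0.05^(1/n). The chance of at least one event at true rate p is 1 − (1 − p)^n.

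| n | Upper bound, 0 events | p = 5% | p = 10% | p = 20% |
|---|---|---|---|---|
| 5 | 45.1% | 23% | 41% | 67% |
| 9 | 28.3% | 37% | 61% | 87% |
| 10 | 25.9% | 40% | 65% | 89% |

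A clean review of 5 to 9 patients gives little reassurance, though 10 patients give only slightly more than 9. The review would mainly serve to catch a common problem that is already visible. With no patients treated it adds nothing.

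**The case against.** The strongest reply is that this is a design choice. The bullet is introduced as an alternative: published evidence at 4 units stands in for ten in-house patients at 4 units. Both routes then go one unit beyond the evidence they rest on, and both keep the 10-patient assessment before 6. That stands. The two bullets do not contradict each other, and section 4.1 does not contradict them because it cross-refers to 5.2.

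Two stronger readings are tempting, and the protocol supports neither.

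- A reader might infer that the publication route bypasses the only check for thrombocytopenia, since the word appears only in connection with the cap. But section 10.1 and Appendix I provide for serial platelet count monitoring, and section 11.1 brings abnormal laboratory findings into adverse event review. The Committee's monthly remit is also not confined to hemolysis.
- A reader might infer that the Committee has no discretion to hold the cap at 4. The wording does not clearly go that far. The Committee is the body that approves whole blood use and raises the cap. Section 8.4.1 ties the larger amount to its being judged safe, although it speaks of 6 units. The medical monitor can stop the study on any safety concern.

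It is also fair to say that a review of a handful of patients is weak evidence.

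What survives is narrow: none of these safeguards is linked to the decision to go to 5 units on publication. The section 12.5 reaction rule would not fill the gap, because it needs a clinical syndrome as well as evidence of hemolysis.

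**Conclusion.** The point holds as a small weakness in how the rule is worded. Review of the study's own patients is a written condition of the 4-to-5 step for 10 patients on the main route and for none on the publication route, when 0 to 9 may have been treated. The patients are not unmonitored; the monitoring is simply not tied to this step.

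The practical effect is limited to one unit of about 250 mL, given only if needed, and only if publication comes before the 10th whole blood patient. The 3.7 to 4.9 months for that window rest on the assumed even accrual over 18 to 24 months; the reading of the two routes rests on no assumption. This is a cheap improvement, worth making because the data are already collected.

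**What to change.** In the second bullet of section 5.2, where the rise to 5 units is granted, replace *will allow* with *may allow, after reviewing the hemolysis labs and platelet counts of all whole blood patients treated to date and finding no evidence of greater risk than with similar amounts of component therapy*. This keeps the comparative standard of the first bullet. Leave the publication route, the caps and the 10-patient assessment before 6 units as they are.

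The cost is one sentence. No new tests are needed, and the Committee already monitors monthly. The early increase might wait a short time for one Committee review, and that review is of little value if very few patients have been treated.

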6 PATIENT SELECTION

6.1 Study Population

All trauma patients who present with SBP<100 who require activation of the massive transfusion protocol and who do not have severe burns (>20% total body surface area) will be eligible for enrollment.

Enrollment of male and female patients:

PI: [name]

At UCLA and at least two other institutions²⁸ the standard of care for traumatic resuscitation for adult males is either:

- 1) Low anti-A anti-B titer (<1:100) group O+ whole blood
or, when whole blood is not available,
- 2) Component therapy, consisting of group O+ PRBCs, group AB or A plasma, and untyped platelets

The standard of care for adult females is component therapy, consisting of group O- PRBCs, group AB or A plasma, and untyped platelets. Group O- whole blood is not available at our institution at this time. During a critical traumatic resuscitation, it is often impossible to determine precise age and menopausal status before initiation of transfusion. In order to avoid any possibility of alloimmunization of reproductive-age females, the UCLA Blood and Blood Derivatives Committee has approved group O+ whole blood only for use in males.

The index and control groups in the study therefore consist of:

- 1) Index group: male trauma patients presenting with SBP<100 who require activation of the massive transfusion protocol and who do not have severe burns >20% TBSA who receive whole blood;
- 2) Prospective control group: Prospectively-identified cohort of patients who present during the study with SBP<100 who require activation of the massive transfusion protocol and who do not have severe burns >20% TBSA but who are either not eligible or not able to receive whole blood. This category consists of patients who are female (who are not eligible to receive whole blood) and male patients who present when whole blood is out of stock;
- 3) Historical control group: male trauma patients who presented with SBP<100 who required activation of the massive transfusion protocol and who did not have severe burns >20% TBSA who received component therapy for traumatic hemorrhage requiring massive transfusion protocol activation, during the 5 years prior to initiation of the study.

A mixed effects linear regression model will be used to adjust for confounding variables, including sex.

Enrollment of patients of unknown precise age:

Due to the emergent nature of a critical code trauma activation, it is often not possible to determine exact age of patients prior to initiating treatment, including transfusion, for

PI: [name]

hemorrhaging patients. Patients who appear to be adults, ie over age 18, will be eligible for inclusion in the study. Every effort will be made to ensure that patients enrolled are at least 18 years old, while respecting the necessities of clinical care. However, we acknowledge it is possible that there may be an instance where a patient is included who is not over age 18.

6.2 Inclusion Criteria

All trauma patients who present with SBP<100 who require activation of the massive transfusion protocol and who do not have severe burns (>20% total body surface area) will be eligible for enrollment. The study plans to include all such patients who present during the study period of approximately 2 years.

Within this group of patients, all adult male patients who received or will receive whole blood are eligible for inclusion in the whole blood group. All adult male patients who received or will receive component therapy initially are eligible for inclusion in the component therapy group. All adult female patients are eligible for inclusion in the component therapy group.

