RATIONALE	Our study will test the feasibility of providing whole blood (WB) for resuscitation of adult male trauma patients in hemorrhagic shock and determine the effects of WB on clinical outcomes as well as the effects on coagulation, fibrinolysis, and inflammation, and hemolytic transfusion reactions compared to standard blood component therapy.
STUDY DESIGN	Prospective cohort study
PRIMARY OBJECTIVE	1. Compare volume of blood transfusion within 24 hours of admission between patients receiving whole blood and standard component therapy.
SECONDARY OBJECTIVES	The study will also compare: 1. Functional coagulopathy as measured by thromboelastography;

	
 2. 30-day mortality; 3. Number of units of blood products transfused by component/product; 4. Complications; 5. Hemolysis; 6. Wastage of blood units.
NUMBER OF PATIENTS	
Whole blood arm - 49 male patients over apparent age 18. Component therapy arm –49 male and female patients over apparent age 18.

PATIENT SELECTION CRITERIA	
Inclusion Criteria:
 
 • Whole blood arm: Male trauma patients over apparent age 18 with massive transfusion activation and presenting systolic blood pressure <100, who are receiving or will receive whole blood for initial resuscitation • Component therapy arm: Male and female trauma patients over apparent age 18 with massive transfusion activation and presenting systolic blood pressure <100, who have received, are receiving or will receive component therapy for initial resuscitation. 
Exclusion Criteria:
 
 • Patients with burns over >20% total body surface area
TEST PRODUCT, DOSE, AND ROUTE OF ADMINISTRATION	
Group O+ whole blood stored at 1-6 °C for up to 10 days. Patients may receive up to 4 units during the initial phase of the proposed study, to be increased to up to 6 units (see 5.2 Safety Evaluations) Product is administered to replace ongoing blood loss and restore/maintain hemodynamic stability and hemostasis. Product will be transfused intravenously as needed during initial traumatic resuscitation only. Following administration of whole blood if further transfusion is needed during initial trauma resuscitation, or after resuscitation is completed, the patient will receive standard

PI: [name]

	component therapy (packed red blood cells, plasma and platelets in a 1:1:1 ratio).

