13 PROTOCOL VIOLATIONS

A protocol violation occurs when the patient or Sponsor/Investigator fails to adhere to significant protocol requirements affecting the inclusion, exclusion, patient safety and primary endpoint criteria. Protocol violations for this study include, but are not limited to, the following:

- Failure to meet inclusion/exclusion criteria
- Switching from component therapy to whole blood

Failure to comply with Good Clinical Practice (GCP) guidelines will also result in a protocol violation. The Sponsor/Investigator will determine if a protocol violation will result in withdrawal of a patient.

When a protocol violation occurs, it will be discussed with the Sponsor/Investigator and a Protocol Violation Form detailing the violation will be generated. This form will be signed by a Sponsor/Investigator or representative. A copy of the form will be filed in the site's regulatory binder and in the Sponsor/Investigator's files.

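### A man who starts on components and then receives whole blood meets the definition of both arms (sections 6.2, 6.1 and 8.1), and his arm or inclusion can be settled after his 24-hour volume is known

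*Protocol*

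**What the plan says.** Section 6.2 has three sentences that sort patients into groups:

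- Men, whole blood: "all adult male patients who received or will receive whole blood are eligible for inclusion in the whole blood group".
- Men, components: "All adult male patients who received or will receive component therapy initially are eligible for inclusion in the component therapy group".
- Women: "All adult female patients are eligible for inclusion in the component therapy group".

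Section 6.1 defines the index group as men who receive whole blood, again without a condition on order. Of the prospective controls it says "This category consists of patients who are female (who are not eligible to receive whole blood) and male patients who present when whole blood is"; the sentence ends by naming a stock-out. Section 8.1 enrols men in the whole blood group if whole blood was or will be given for the resuscitation. It enrols men in the component group if they present when whole blood is unavailable, and it includes eligible women in the component group without reference to product.

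The synopsis is narrower. Its whole blood arm takes men "who are receiving or will receive whole blood for initial resuscitation", and its component arm takes men and women "who have received, are receiving or will receive component therapy for initial resuscitation". Sections 5.1 and 15.3 also compare by product received for or during initial resuscitation. Section 15.1 groups by product received, with no order.

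Two sections foresee departures. Section 13 lists "Switching from component therapy to whole blood" as a protocol violation and leaves the decision on withdrawal to the sponsor-investigator. Section 5.2 provides that "The occurrence of any whole blood transfusion given to patients other than adult male trauma patients will also be recorded". Neither says in which arm such a patient is analysed. Under 12.4, patients who withdraw are replaced. Under 8.2, the study is not blinded.

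**The concern.** In a cohort without randomisation the arm label is the exposure, so it should be fixed by one rule that can be applied at baseline. Here the men's whole blood rule looks at any receipt and the men's component rule looks at what came first. One kind of patient satisfies both, and it is a kind the protocol itself expects.

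Three outcomes are open for him: whole blood arm, component arm, or withdrawn and apparently replaced. The choice falls to someone who knows the treatment and may already know the 24-hour volume, which is the primary endpoint. Withdrawal would also cut across the aim in 6.2 of including every eligible patient in the study period.

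If he is counted as whole blood, the components he was given first count as whole blood arm volume, and his membership of that arm depends on surviving and still bleeding long enough to be switched. Patients who die before any switch remain controls.

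**Working it through.** **1. The protocol's own numbers.** Synopsis and section 15.5 (sample size): 49 enrolled per arm, about 18 with severe TBI. 49 − 18 = 31, and 31 / (1 − 18/49) = 49, so the figure reproduces. At the stated 35% and 40% TBI, 49 × 0.65 = 31.9 and 49 × 0.60 = 29.4 remain. One patient is 1/31 = 3.2% of an arm.

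**2. The rules applied to each kind of patient.**

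| Patient | 6.2 | Synopsis | Result |
|---|---|---|---|
| Man, whole blood first, components later | Whole blood only | Whole blood arm intended; it foresees components afterwards | Clear |
| Man, components only | Component only | Component | Clear |
| Man, components first, then whole blood in the initial resuscitation | Both | Both products given in the qualifying window | Two arms |
| Woman, components first, then whole blood | Component | Component criterion met; whole blood arm is male only | One arm |
| Woman, whole blood only | Component | Component criterion not met; whole blood arm is male only | 6.2 and synopsis conflict |

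For the third row, 6.1 and 8.1 give the same double answer: he presented when whole blood was unavailable (control) and later received it (index). The synopsis restricts whole blood to initial resuscitation, so a switch made according to the plan falls inside the very window used to define the arms. That is why the initial-resuscitation wording does not separate them.

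**3. Direction if switchers are moved to whole blood.** Take 31 whole blood patients with mean m, and 31 component patients with mean c, one of whom is a switcher with volume V. Moving him raises the whole blood mean by (V − m)/32 and lowers the component mean by (V − c)/30. With no true difference (m = c) and V lying x standard deviations (SD) above the mean, the spurious difference is x × (1/32 + 1/30) = 0.065x SD. The protocol gives no distribution, so x is an assumption: x = 0 gives 0, x = 1 gives 0.065 SD, x = 2 gives 0.129 SD. For comparison, 31 per arm has 80% power at d = (1.960 + 0.842) × √(2/31) = 0.71 SD (two-sided 0.05 assumed). One switcher at x = 1 is therefore 0.065/0.71, about 9% of that difference. When V is above the mean the shift makes whole blood look as if it needs more volume.

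**4. Cost of leaving switchers in the component arm.** If k of 31 in one arm in fact had the other treatment and the effect dilutes in proportion, power = Φ(0.7116 × (1 − k/31) × √(31/2) − 1.960). This gives 80% at k = 0, 77% at k = 1 and 72% at k = 3. Removing k patients from one arm instead gives 79% at k = 1 and 78% at k = 3. The values of k are illustrations. Proportional dilution treats a switcher as if he had had whole blood only, so it probably overstates the loss. The 80% itself cannot be checked, because the protocol states neither effect size nor SD.

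**The case against.** The strongest reply is that the protocol's intent is clear enough. Whole blood is confined to initial resuscitation, which the synopsis says is usually over within a few hours. The primary comparison is worded around that phase. Sections 6.1 and 8.1 define male controls by stock at presentation, which is a baseline fact. A switch should be uncommon: section 8.4 gives an average of 48 hours before a newly donated unit is available, and section 13 classes the switch as a violation. Handling of violators commonly belongs in the SAP, which section 15 says will be written before the final analysis.

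Much of this stands. A reader might infer from 6.2 that the protocol adopts an exposure of whole blood at any time in the 24 hours; the synopsis, 5.1 and 15.3 do not support that. The open case is a man given both products within a short window, and it is probably rare. Rarity is not certain, though, because units already collected, or held in the second of the two storage places named in 8.4, can arrive sooner than a new donation.

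What does not stand is the claim that intent settles the arm. Sections 6.1 and 8.1 pair their baseline rule for controls with a whole blood rule that has no condition on order, so they repeat the conflict. Calling the switch a violation gives no analysis arm. Nor is this detail deferred to the SAP: group membership is already fixed in the eligibility text, in ways that disagree.

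**Conclusion.** The point holds for men. Sections 6.2, 6.1 and 8.1 give two arms to a man who starts on components and then receives whole blood, and no section decides between them. Sections 13, 12.4 and 8.2 together allow his arm or his inclusion to be decided once his volume is known.

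For women the point is smaller and separate. A reader might infer that a woman given whole blood also falls into two arms. She cannot, because the whole blood group is male only. What remains is that 6.2 admits her as a control whatever she received, while the synopsis requires component therapy for initial resuscitation. That is possible misclassification, and 6.2 makes her eligible rather than certain to be analysed as a control.

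On size, the protocol gives no count of switchers and supports no estimate. Each is about 3% of a 31-patient arm. A reader might also infer an immortal-time bias that flatters whole blood. For a 24-hour volume endpoint the likely direction is the reverse: patients who go on bleeding would move into whole blood, and early deaths with little transfused would stay as controls. This rests on the assumption, not shown in the protocol, that switchers have above-average volumes.

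The text should be corrected, because the defect is certain on reading even though its frequency is not.

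**What to change.** Use one classification rule, in the same words, in the synopsis and in sections 6.1, 6.2, 8.1 and 15.1: *a patient's arm is the product of the first red-cell-containing unit (whole blood or PRBC) started after arrival; the patient stays in that arm and in the analysis whatever is given later.*

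Apply it to women as well, replacing the unconditional sentences in 6.2 and 8.1. A woman whose first unit is a component is a control, even if whole blood follows. A woman whose first unit is whole blood is reported under the safety item in 5.2 and is not a component control.

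In section 13, record switching as a deviation, but state that it is no ground for changing arm, or for removing or replacing the patient in the analysis.

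The cost is a few sentences in six places and one data item, since the chart-review list in section 10.1 does not name the type and time of the first unit. The statistical downside is that a few switchers stay in the component arm and slightly dilute the contrast. The rule governs analysis grouping only and changes nothing about treatment.
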